7.1.3 Grading and Relationship to Study Procedure

The descriptions and grading scales found in the CTEP Version 4 of the NCI Common Terminology Criteria for Adverse Events (CTCAE) will be utilized for AE reporting. CTEP Version 4 of the CTCAE is identified and located at:

http://ctep.cancer.gov/protocolDevelopment/electronic_applications/ctc.htm.

AEs not covered by specific terminology listed should be reported with common medical terminology and documented according to the grading scales provided in the CTCAE Version 4.

The relationship of event to study procedure will be documented by the Investigator as follows:

- **Unrelated:** The event is clearly related to other factors such as the participant's clinical state, other therapeutic interventions or concomitant drugs administered to the participant.
- **Unlikely:** The event is doubtfully related to investigational agent(s). The event was most likely related to other factors such as the participant's clinical state, other therapeutic interventions, or concomitant drugs.
- **Possible:** The event follows a reasonable temporal sequence from the time of drug administration but could have been produced by other factors such as the participant's clinical state, other therapeutic interventions or concomitant drugs.
- **Probable:** The event follows a reasonable temporal sequence from the time of drug administration and follows a known response pattern to the study drug. The event cannot be reasonably explained by other factors such as the participant's clinical state, therapeutic interventions or concomitant drugs.

- **Definite:** The event follows a reasonable temporal sequence from the time of drug administration, follows a known response pattern to the study drug, cannot be reasonably explained by other factors such as the participant's condition, therapeutic interventions or concomitant drugs; AND occurs immediately following study drug administration, improves upon stopping the drug, or reappears on re-exposure.

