We hypothesize that pyloric botulinum toxin injection does not prevent delayed gastric emptying and is an unnecessary portion of the minimally invasive esophagectomy. If it is found that botulinum toxin injection does not lead to lower rates of delayed gastric emptying, then this procedure may be omitted, saving cost and side effects associated with the medication, and potential side effects of employing a pyloric drainage procedure, including pyloric edema, dumping syndrome and bile reflux. Pyloric edema from receiving botulinum toxin injection may actually cause delayed gastric emptying. The current rates of pyloric edema, dumping syndrome, and bile reflux are unclear at this time, and will be directly assessed in this study during the nuclear medicine emptying study.

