7.1.4 Reporting Adverse Events

Table 43 Guidelines for Routine Adverse Event Reporting for Phase 2 Studies (Regardless of Expectedness)

Attribution	Grade 1	Grade 2	Grade 3	Grade 4
Unrelated			X	X
Unlikely			X	X
Possible	X	X	X	X
Probable	X	X	X	X
Definite	X	X	X	X

Routine AEs occurring between the starting date of intervention until 30 days after the last intervention, or until the event has resolved, the study participant is lost to follow-up, the start of a new treatment, or until the study investigator assesses the event(s) as stable or irreversible, will be reported. New information will be reported after it is received.

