9.4.1 Adverse Events

The adverse events will be reported by grade using frequencies and relative frequencies. Additionally, the study will be monitored by the RPCI Data and Safety Monitoring Committee, which will assess the progress of the study, the safety data, and critical efficacy endpoints.

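### Read literally, Sections 7.1.3 and 7.1.4 filter out non-serious grade 1-2 adverse events in the no-botulinum arm while reporting those judged at least possibly related in the Botox arm

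*Combined protocol and SAP*

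**What the plan says.** All references are to the combined protocol and SAP.

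- **Object of attribution.** The lead-in of Section 7.1.3 reads "The relationship of event to study procedure will be documented by the Investigator as follows", and the section heading also names the study procedure.
- **Definitions.** *Possible* is worded "The event follows a reasonable temporal sequence from the time of drug administration but could have been produced by other factors". *Probable* and *definite* keep the same timing rule and add that the event "follows a known response pattern to the study drug". *Unlikely* is worded "The event is doubtfully related to investigational agent(s". *Unrelated* names no drug and requires a clear link to other factors.
- **Reporting filter.** The table in Section 7.1.4 (printed as Table 43), titled "Guidelines for Routine Adverse Event Reporting for Phase 2 Studies (Regardless of Expectedness", marks grades 3 and 4 for *unrelated* and *unlikely*, and grades 1 to 4 for *possible*, *probable* and *definite*.
- **Reporting window.** Section 7.1.4 covers "Routine AEs occurring between the starting date of intervention until 30 days after the last intervention". It does not say what counts as the intervention in the no-botulinum arm.
- **Control arm.** Under Section 6.3 it has the same operation without the injection. No sham is described. Section 4.1 states that the surgeon is not blinded.
- **Analysis.** Section 9.4.1 says "The adverse events will be reported by grade using frequencies and relative frequencies" and does not mention treatment arm.
- **Stated benefit.** Section 1.2 says that omitting the injection may mean "saving cost and side effects associated with the medication".

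**The concern.** A safety comparison between randomized arms needs the same ascertainment rule in both. Here the rule that decides whether a mild event enters the routine adverse event data runs through a causality judgement, and the categories that admit grade 1-2 events are defined by exposure to the drug. Only one arm has that exposure at surgery. The same mild hoarseness or weakness could therefore be reported for a Botox patient and dropped for a control patient. The surgeon knows the arm, so the judgement may also be made with that knowledge.

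What is at stake is the descriptive low-grade safety summary. One argument for omitting the injection is that it spares patients the side effects of the medication. A table built on this filter could appear to support that argument when the true rates are equal. Section 11.1 sends adverse event data for the monitoring committee through a separate system from the other case report data, so the data stream subject to the filter is the one prepared for that committee.

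**Working it through.** The plan gives no figure on this point, so there is none to reproduce. The check has two logical steps and one illustration of size.

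**Step 1. Cross the definitions (7.1.3) with the filter (7.1.4) for a patient who had no injection.**

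| Category | Anchor in 7.1.3 | Grade 1-2 reportable in 7.1.4 | Literally open to a control patient at surgery |
|---|---|---|---|
| Unrelated | other factors | no | yes |
| Unlikely | investigational agent | no | yes |
| Possible | time of drug administration | yes | no |
| Probable | drug timing and response pattern | yes | no |
| Definite | drug timing and response pattern | yes | no |

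On the literal reading, the rows open to control patients are exactly those in which grades 1-2 are not reportable. If the heading is followed instead, a control event could be attributed to the operation and reported. The section supports both readings, and they give different control-arm data.

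**Step 2. Ask what captures low-grade events by another route.** Section 7.1 collects clinical events of interest in REDCap with no grade or attribution filter, in both arms. Compare its named items with the seven toxin-spread symptoms in Section 7.1.2:

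- asthenia, diplopia, ptosis and urinary incontinence: not named;
- dysphonia: not named, although one OES18 item asks about trouble talking in the week before Postoperative Visit #2;
- dysphagia: partly covered by trouble eating and difficulty swallowing saliva;
- breathing difficulties: named only as respiratory failure requiring reintubation.

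The Section 7.1 list is open-ended, but nothing requires the unnamed symptoms to be entered.

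**Step 3. Illustrate the size.** Inputs: 50 patients randomized 1:1 (Section 9.1), so 25 per arm. Let r be the true share of patients with a grade 1-2 event, equal in both arms, and s the share of Botox-arm events judged at least possible. The documents give neither, so both are assumptions.

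Expected reported patients are 25 × r × s on Botox and 0 on control. For x/25 against 0/25 the two-sided Fisher p is 2 × C(25,x) / C(50,x). With r = 0.40, 10 patients in each arm have an event:

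| s | Reported, Botox v control | Fisher p |
|---|---|---|
| 10% | 1/25 v 0/25 | 2 × 25/50 = 1.0 |
| 30% | 3/25 v 0/25 | 0.23 |
| 40% | 4/25 v 0/25 | 0.11 |
| 50% | 5/25 v 0/25 | 2 × 53130/2118760 = 0.0502 |
| 70% | 7/25 v 0/25 | 2 × 480700/99884400 = 0.0096 |
| 80% | 8/25 v 0/25 | 2 × 1081575/536878650 = 0.0040 |

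Over a wider grid (r from 40% to 80%, s from 10% to 50%), the expected Botox count runs from 25 × 0.40 × 0.10 = 1.0 to 25 × 0.80 × 0.50 = 10.0. The smallest x with p at or below 0.05 is 6 (p = 0.022). The binomial chance of reaching it is about 0% at 40% × 10%, 16% at 60% × 25%, 38% at 40% × 50%, 81% at 60% × 50% and 97% at 80% × 50%. The plan specifies no test on adverse events, so these figures only show how far a descriptive table might mislead when the true difference is zero.

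**The case against.** The other side has real force, and it limits the point in several ways.

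- **A reader might infer that attribution rests on drug exposure alone, so a control event can never be *possible*.** The documents do not go that far. The heading and lead-in of 7.1.3 say study procedure, *unrelated* needs a clear other cause, and Section 6.5 allows endoscopic botulinum later in either arm.
- **A reader might infer that mild control-arm events are lost altogether.** They are not. Section 6.3 has adverse events recorded in both arms, Section 7.1 captures many mild symptoms unfiltered, Section 7.2.2 reports all new serious events to day 90, and grade 3-4 events are reportable in every category. In the Botox arm, too, low-grade events judged *unlikely* or *unrelated* are not reported.
- **A reader might infer that Section 9.4.1 prescribes pooling.** It is silent on arm. The by-arm statement in Section 9.4 covers the secondary outcomes only.
- **A reader might infer that serious events share the bias.** Section 7.3 governs only how long related serious events are followed, not whether they are reported.
- **The benefit claim in Section 1.2 does not rest on this table alone.** Pyloric edema, dumping and bile reflux are to be assessed at the nuclear medicine study, done in both arms. Comparative low-grade toxicity is not a stated objective.
- **The size is assumed.** Section 7.1.2 describes toxin spread as rare. At low attribution shares the distortion is one or two patients.

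All of this stands and narrows the scope. It does not remove the contradiction within 7.1.3 or make the reporting filter the same in both arms. The other capture routes also miss most of the symptoms that the protocol itself associates with the toxin.

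**Conclusion.** The point holds for routine, non-serious grade 1-2 adverse events, on a literal reading and before any later endoscopic botulinum. It bears mainly on events outside the Section 7.1 list, including asthenia, diplopia, ptosis, dysphonia and urinary incontinence. A low-grade table by arm would be biased toward an excess on Botox. The amount cannot be determined from the documents: under the assumed 40% rate in both arms, it ranges from 1/25 to 8/25 against 0/25 as the attribution share goes from 10% to 80%.

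A prediction that the trial will show a significant false excess is not supported. The rates are assumed, no test is planned, and sites may follow the heading rather than the definitions. The primary endpoint, alpha, power and sample size are untouched.

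**What to change.** 1. **Section 7.1.4, reporting table.** Apply one attribution-free grade threshold to both arms for routine adverse events. Either report all grades, or report all grades of the toxin-spread symptoms named in Section 7.1.2 plus grade 3 and above for everything else. State what starts the reporting window in the no-botulinum arm.
2. **Section 9.4.1.** Tabulate adverse events by treatment arm and grade, with attribution to botulinum as a separate descriptive field that does not decide inclusion.
3. **Section 7.1.3.** Reconcile the definitions with the heading and lead-in. If relatedness is tied to the operation in both arms, many ordinary postoperative events will become *possible*. Keeping botulinum attribution as its own field prevents that from blurring the drug signal.

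The cost is protocol wording and somewhat more adverse event entry in both arms. The schedule in Table 2 already has adverse events assessed on the day of surgery and at each later contact, so no visit or procedure is added.

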7.1.4 Reporting Adverse Events

Table 43 Guidelines for Routine Adverse Event Reporting for Phase 2 Studies (Regardless of Expectedness)

Attribution	Grade 1	Grade 2	Grade 3	Grade 4
Unrelated			X	X
Unlikely			X	X
Possible	X	X	X	X
Probable	X	X	X	X
Definite	X	X	X	X

Routine AEs occurring between the starting date of intervention until 30 days after the last intervention, or until the event has resolved, the study participant is lost to follow-up, the start of a new treatment, or until the study investigator assesses the event(s) as stable or irreversible, will be reported. New information will be reported after it is received.

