Improving gastric emptying is crucial to not only maintaining independent nutrition, but also in preventing devastating pulmonary complications including aspiration and subsequent pneumonia. In the era of open esophagectomy, several types of drainage procedures were employed during esophagectomy in an attempt to prevent gastric outlet obstruction. These include pyloroplasty (full-thickness longitudinal incision closed transversely), pyloromyotomy (incision through muscle only, preserving integrity of mucosal layer), and finger fracture (manual pressure on the pylorus, causing muscle disruption). Other surgeons elected not to perform any type of drainage procedure. Advocates of the “no drainage” procedure believed that surgical manipulation of the pylorus during drainage procedures leads to short-term inflammation and edema, which may *cause* gastric outlet obstruction despite that this procedure is designed to prevent such occurrence. In addition, pyloric drainage procedures may lead to dumping syndrome, bile reflux, or leak at the pyloroplasty site, leading to intra-abdominal or intra-thoracic sepsis and even death (3). Possible long-term side effects include scar or stricture formation. Alternatively, no drainage procedure may cause gastric outlet obstruction, leading to inability to tolerate oral diet, aspiration, and pneumonia. Whether or not to perform a pyloric drainage procedure is controversial.

With newer minimally invasive esophagectomy techniques, many surgeons omitted drainage procedures, as they are technically challenging to perform minimally invasively. Other surgeons use botulinum injection at the pylorus as a minimally invasive pyloric drainage procedure, with

the theory this relaxes the muscle without causing inflammation, edema, or risk of leak. Intraoperative botulism toxin injection is safe and simple to perform, without significantly adding to the total operative time. It does however add significant cost to the procedure, approximately \$1,000 per treatment (1). Botulinum toxin injection into the pyloric sphincter has a pharmacologic duration of three to five months (4).

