6.5 Criteria for Retreatment

- Patients with “severe” delayed gastric emptying assessed radiographically or clinically at any time will be considered for endoscopic procedures for gastric outlet obstruction, including pyloric botulinum toxin injection or balloon dilation, or operative procedure. This is irrespective of whether a patient was initially treated with botulinum toxin at the minimally invasive esophagectomy; patients randomized to the botulinum toxin group may undergo additional botulinum toxin injection endoscopically. The maximum dose of botulinum toxin a patient may receive for this study in the three-month period is 300 units. Each of these procedures- when a patient undergoes a therapeutic endoscopic procedure or returns to the operating room- will be defined as a secondary procedure.
- Development of “severe” delayed gastric emptying as assessed by nuclear medicine study will be considered a failure of the experimental procedure and will be included in the primary analysis. Requirement for secondary procedure or development of “severe” delayed gastric emptying as assessed by parameters other than the nuclear medicine study will be included in the secondary analysis.
- Patients with “moderate” delayed gastric emptying assessed radiographically or clinically at any time will be considered for initiation of promotility agents. Development of “moderate” delayed gastric emptying will be included in the secondary analysis.

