6.7 End of Study Visit

- At day #90 (\pm 7 days), an end of study phone call will be conducted by the study coordinator. The purpose of this call is to inquire about any subsequent procedures the patient may have undergone related to delayed gastric emptying or esophagectomy, nutrition assessment to determine if the patient continues to require supplemental jejunal feeds, any persistent clinical symptoms of delayed gastric emptying, including any subsequent pneumonia, aspiration events, respiratory failure, nausea, vomiting, ability to eat solid food or drink liquids or having any trouble eating, early satiety, difficulty swallowing saliva, noticing bile or green staining on pillow while sleeping, experiencing acid indigestion or heartburn, or pain with eating, concomitant medications and Clinical Events of Interest and adverse events will be assessed. If the patient indicates continued use of tube feeds, the study coordinator will alert the dietitian to call the patient for further evaluation of the percentage of tube feeds versus oral intake. If the patient is no longer using jejunal feeds, the study coordinator will mark down “100% oral intake.

The schedule of procedures and observations for this study is summarized in **Table 2** below.

Table 2 Schedule of Procedures and Observations

Evaluation	Baseline ¹	Day of Surgery	Inpatient Postoperative Course ² (Surgery to Discharge)	Postoperative Visit #1 ³ ± 14 days	Postoperative Visit#2 ³ ± 14 days	End of Study phone call Day#90 (± 14 days)
Medical History, Pre-Existing Conditions (including smoking status, diabetes)	X					
ECOG Performance Status	X					
Multidisciplinary Evaluation and neoadjuvant therapy for esophageal carcinoma	X					
Physical Examination, including vital signs ⁴	X	X	X	X	X	
Hematology ⁵	X		X		X	
Chemistry ⁶	X		X		X	
Sign study informed consent, if eligible based on above factors	X					
Minimally invasive esophagectomy with or without pyloric drainage procedure		X				
Fasting glucose				X As indicated)		
Chest X-Ray, CT chest			X (As indicated)		X (As indicated)	

Evaluation	Baseline ¹	Day of Surgery	Inpatient Postoperative Course ² (Surgery to Discharge)	Postoperative Visit #1 ³ ± 14 days	Postoperative Visit#2 ³ ± 14 days	End of Study phone call Day#90 (± 14 days)
Gastrograffin swallow evaluation ¹² /CT esophagram			X ^{12a}			
Nuclear Medicine Emptying Study ^{10, 11}				X ¹¹ (Phone call prior to give instructions)		
Clinical Evaluation of Symptoms			X	X ¹¹	X	X

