Medical evaluation (signs of pneumonia, aspiration)			X	X	X	
Nutrition evaluation ¹³	X (As indicated)		X ¹⁴	X	X	X (As indicated)
EORTC QLQ OES18 Questionnaire ¹⁰ See Appendix D					X	
Pregnancy Test ⁷ (Urine)	X					
Electrocardiogram, Chest x-ray, and/or Pulmonary Function tests	X (As indicated)					
Speech therapy evaluation			X (As indicated)			
Concomitant Medications	X ⁸	X	X	X	X	X
Clinical Events of Interest and AEs		X ⁹	X	X	X	X

Evaluation	Baseline ¹	Day of Surgery	Inpatient Postoperative Course ² (Surgery to Discharge)	Postoperative Visit #1 ³ ± 14 days	Postoperative Visit#2 ³ ± 14 days	End of Study phone call Day#90 (± 14 days)
Fasting glucose (for patients with diabetes)					X (As indicated)	

1 Baseline evaluations will be performed prior to the participant's scheduled minimally invasive esophagectomy and will be confirmed before surgery (Preoperative workup and multimodality therapy for esophageal cancer as standard of care at Roswell Park and based upon the NCCN guidelines for esophageal cancer. Refer to Section 6.2).

2 Patients will follow the standard of care postoperative pathway for minimally invasive esophagectomy.

3 Initial Standard of Care postoperative follow-up visit (Postoperative Visit #1) after hospital discharge, and then again at Postoperative Visit #2 if the postoperative course is uncomplicated. If complications arise, patients may be seen more often in follow-up. Patients will be followed for data collection for 90 days following surgery.

4 Vital signs (temperature, heart rate, respiratory rate, blood pressure), body weight and, height. Height collected at baseline only.

5 If indicated by the anesthesia pre-op assessment- Hematology: CBC with automated differentials (WBC, RBC, HGB, HCT, platelet, MCV, MCH, MCHC, % neutrophils, absolute neutrophils, % monocytes, absolute monocytes, % eosinophils, absolute eosinophils, % basophils, absolute basophils, % lymphocyte, absolute lymphocyte, platelet confirmation (as clinically indicated), and differential confirmation (as clinically indicated).

6 If indicated by the anesthesia pre-op assessment - Chemistry: CMP (chloride, CO₂, potassium, sodium, BUN, glucose, calcium, creatinine, total protein, albumin, total bilirubin, alkaline phosphatase, AST, ALT, A/G ratio, BUN/creatinine ratio, osmol (Calc), anion gap), as clinically indicated.

7 To be performed < 1 week prior to scheduled surgery,

8 Medications ongoing, or discontinued, within 1 week prior surgery.

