7.2.2 Reporting Serious Adverse Events

All new SAEs occurring from the date the participant signs the study consent until 90 days after the last intervention or a new treatment is started, whichever comes first, will be reported. The RPCI SAE Source Form is to be completed with all available information, including a brief narrative describing the SAE and any other relevant information.

SAEs occurring after the 90 day follow-up period that the investigator determines to be possibly, probably or definitely related to the study intervention should be reported.

SAEs that are unexpected and possibly, probably or definitely related must be reported as an Unanticipated Problem. Please refer to **Section 7.4** for details on reporting Unanticipated Problems.

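### The protocol gives three different end points for adverse-event capture and leaves 'last intervention' and 'new treatment' undefined, so the routine-event window can vary with re-treatment

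*Combined protocol and SAP*

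**What the plan says.** Four parts of the combined protocol and SAP bear on how long adverse events are captured.

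- **Reporting rule, section 7.1.4.** It covers "Routine AEs occurring between the starting date of intervention until 30 days after the last intervention". The same sentence then lists further end points: resolution, loss to follow-up, "the start of a new treatment, or until the study investigator assesses the event(s) as stable or irreversible, will be reported". It does not say which of these prevails.
- **Recording rule, section 6.3 and Table 2 footnote 9.** Recording runs from entry to the operating room to a postoperative follow-up that is given no date.
- **Assessment schedule, section 6.7 and Table 2.** At the day-90 call, "concomitant medications and Clinical Events of Interest and adverse events will be assessed". The Table 2 row "Clinical Events of Interest and AEs" is marked at surgery, the inpatient course, both postoperative visits and the call. The call window is ±7 days in the section 6.7 text and ±14 days in the Table 2 header.
- **Serious events, section 7.2.2.** These are reported from consent "until 90 days after the last intervention or a new treatment is started, whichever comes first, will be reported". Later serious events judged related are also to be reported.

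Section 6.5 allows further procedures for severe delayed emptying whatever the first assignment; for example, "patients randomized to the botulinum toxin group may undergo additional botulinum toxin injection endoscopically". It calls each of these a secondary procedure and does not say whether that is an intervention or a new treatment for sections 7.1.4 and 7.2.2.

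Section 9.4.1 says "The adverse events will be reported by grade using frequencies and relative frequencies". It mentions neither a time window nor treatment arm.

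**The concern.** A comparison of adverse-event frequencies is fair only if every patient is at risk of having an event counted over the same period. Here the period turns on two undefined terms, and both are touched by re-treatment. Re-treatment follows from delayed emptying, the outcome under study, and section 9.4 expects additional procedures to be less frequent with botulinum. A window tied to re-treatment is therefore tied to outcome and possibly to arm.

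There is also a practical gap. Two scheduled assessments, Visit #2 and the day-90 call, normally fall after the 30-day limit, so staff who find a new non-serious event there have no clear reporting rule. The control arm adds a further uncertainty: it receives no toxin, so what counts as its intervention, and hence what starts and ends its window, has to be inferred.

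The late period is not obviously irrelevant to the drug. Section 1.1 says that the pyloric injection "has a pharmacologic duration of three to five months".

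**Working it through.** The plan states no figure for this point, so there is none to reproduce. The check is date arithmetic plus one illustration.

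**Inputs from the documents**

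- Routine-event limit: 30 days after the last intervention (7.1.4).
- Serious-event limit: 90 days after the last intervention or a new treatment, whichever is first (7.2.2).
- Follow-up: 90 days (4.2, 6.6).
- Visit #2: usually postoperative week six to eight (6.6), that is day 42 to 56.
- Call: day 90 ±7 (6.7) or ±14 (Table 2).
- Additional-procedure rates from a previous study: 3.9% with botulinum, 15.9% without (9.4).
- Arm size: 50/2 = 25.

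**Assumed:** re-treatment day. The documents give no distribution, so several days are shown.

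**Step 1. Surgery as the only intervention.** The limit falls on day 30, leaving 90 − 30 = 60 follow-up days beyond it. Visit #2 (day 42 to 56) falls after it. So does the call: 90 ± 7 gives day 83 to 97, and 90 ± 14 gives day 76 to 104.

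**Step 2. One re-treatment on day d, under each reading of 7.1.4.** If re-treatment is an intervention, the window ends on day d + 30 (capped at 90). If it is a new treatment that ends the window, the end is the smaller of d and 30.

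| Re-treatment day | End if an intervention | End if a new treatment |
|---|---|---|
| 20 | 20 + 30 = 50 | 20 |
| 45 | 45 + 30 = 75 | 30 |
| 60 | 60 + 30 = 90 | 30 |

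The first reading always moves the end. The second moves it only for re-treatment before day 30.

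**Step 3. Size by arm.** Expected numbers re-treated are 25 × 0.039 = 0.975 with botulinum and 25 × 0.159 = 3.975 without, so about 1 and 4 patients. Mean window end = 30 × (1 − p) + (end if re-treated) × p.

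- Lengthening reading, day 45:
  - botulinum 30 × 0.961 + 75 × 0.039 = 31.8
  - no botulinum 30 × 0.841 + 75 × 0.159 = 37.2
  - difference 5.4 days
- Lengthening reading, day 60:
  - botulinum 30 × 0.961 + 90 × 0.039 = 32.3
  - no botulinum 30 × 0.841 + 90 × 0.159 = 39.5
  - difference 7.2 days
- Closing reading, day 20:
  - botulinum 30 × 0.961 + 20 × 0.039 = 29.6
  - no botulinum 30 × 0.841 + 20 × 0.159 = 28.4
  - difference 1.2 days, in the opposite direction

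**Step 4. The same terms in 7.2.2.** Re-treatment on day 45 would end serious-event reporting on day 45 if it is a new treatment. If it is an intervention, reporting would run to 45 + 90 = day 135. Related serious events after the 90-day period remain reportable.

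**Step 5. Which events are exposed.** Serious events have the longer window of 7.2.2. Clinical events of interest (7.1), which include pneumonia, aspiration, reintubation, nausea and vomiting, go to REDCap with no 30-day limit. What remains is non-serious events that are not clinical events of interest and begin on days 31 to 90.

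**The case against.** The case against making much of this is strong on several counts.

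- A reader might infer that the routine-event window restarts with each re-treatment, so that a patient re-treated on day 50 is observed to day 80, or 80/30 = 2.7 times as long as one who is not. The documents do not say so. Section 6.5 uses the term secondary procedure, and 7.1.4 also names the start of a new treatment as an end point, which points the other way. The title of 6.5, Criteria for Retreatment, makes the restart reading plausible but no more than that.
- A reader might also infer that events collected after day 30 are discarded, or that two thirds of the data are lost. No section excludes a collected event from analysis. Section 7.1.4 governs reporting, and section 11.1 sends adverse-event data to a separate system for the monitoring committee. The 60 of 90 days is a share of calendar time, not of events, and the documents give no event timing from which a loss could be estimated.
- The further end points in 7.1.4 most naturally concern follow-up of events already under way.
- Separate windows for routine and serious events can be deliberate; 7.1.4 already tiers reporting by grade and attribution.
- Duration of drug effect is not timing of onset. Section 7.1.2 puts onset of effect at 1 to 3 days and symptoms of spread at hours to weeks after injection.
- No primary or secondary endpoint, and no stopping rule, uses routine adverse events. Pulmonary complications are compared by arm separately in 9.4.

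All of this limits the size of the problem. It does not remove the disagreement between 7.1.4, 6.3 with footnote 9, and 6.7 with Table 2. Nor does it define the two terms, or supply the window and the split by arm that 9.4.1 lacks.

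**Conclusion.** The point holds as an inconsistency with a minor consequence. The sections give different end points for adverse-event capture. Because the key terms are undefined, re-treatment may lengthen the routine-event window or close it early, so ascertainment could differ by arm.

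The likely size is a few days of mean window: 5.4 days in the day-45 illustration, and smaller and reversed under the closing reading at day 20. These figures rest on rates from a previous study, one re-treatment per affected patient, a single assumed re-treatment day, and 25 patients per arm. The documents do not support a claim that adverse-event rates in general cannot be compared. The exposure is confined to the late, non-serious events identified above, with serious events largely covered, subject to the same undefined terms in 7.2.2.

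**What to change.** 1. Reconcile sections 6.3, 6.7 and 7.1.4 and Table 2 with its footnote 9 to one fixed adverse-event window for every patient in both arms: operating-room entry to postoperative day 90, regardless of re-treatment.
2. Use day 90 as the cutoff, not the date of the call, because the two stated call windows differ. Bring those two into line as well. A call made before day 90 would leave a short tail unobserved, at most 14 days under Table 2.
3. State in 7.1.4 and 7.2.2 whether a secondary procedure counts as an intervention or a new treatment, and what the intervention is in the arm without botulinum.
4. Word the further end points in 7.1.4 so that it is clear whether they apply to follow-up of ongoing events or to capture of new ones.
5. In 9.4.1, report adverse events by arm and grade over the fixed window.

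The change is one of wording, and the visits and the call already exist. The cost is that more low-grade events have to be entered.
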